7.2 Safety Variables

All safety analyses will be performed on the SES in total and by the subpopulations of each indication (subjects treated for nasolabial folds, for marionette lines, and for cheek volume loss).

7.2.1 Primary Safety Variable(s)

AEs will be coded according to the Medical Dictionary for Regulatory Activities (MedDRA). For interim and final analysis the MedDRA version in effect at the time the database is closed will be used. Only TEAEs will be analyzed, which are defined as AEs with onset or worsening at or after the first administration of SMD(s). Each documented worsening of an AE will be counted and presented as separate AE. The start date of the AE will be the date of worsening. If an AE worsens between start and end of this AE it will be considered as new AE entry starting with the date of the worsening (start of new AE = worsening date, stop date of milder AE Episode= date of AE worsening).

The main analysis for the primary safety variable will be:

- Overall incidence of TEAEs.

Further the following AE summary tables will be created displaying incidences of:

- TEAEs, subjects with TEAEs and number of TEAEs by system organ class (SOC) and preferred term (PT).
- TEAEs, subjects with TEAEs by PT.
- TEAEs by worst intensity, subjects with TEAEs by SOC and PT.
- TEAEs by worst causal relationship to RADIÉSSE® (+) Lidocaine, subjects with TEAEs by SOC and PT.
- TEAEs by worst outcome, subjects with TEAEs by SOC and PT.
- TEAEs by affected area, subjects with TEAEs by SOC and PT.
 - TEAEs occurred outside treatment area, subjects with TEAEs by SOC and PT.
 - TEAEs affected right nasolabial fold, subjects with TEAEs by SOC and PT (only for subjects treated at right nasolabial fold).
 - TEAEs affected left nasolabial fold, subjects with TEAEs by SOC and PT (only for subjects treated at left nasolabial fold).
 - TEAEs affected both nasolabial folds, subjects with TEAEs by SOC and PT (only for subjects treated at both nasolabial folds).
 - TEAEs affected right marionette line, subjects with TEAEs by SOC and PT (only for subjects treated at right marionette line).
 - TEAEs affected left marionette line, subjects with TEAEs by SOC and PT (only for subjects treated at left marionette line).

- TEAEs affected both marionette lines, subjects with TEAEs by SOC and PT (only for subjects treated at both marionette lines).
- TEAEs affected right cheek volume, subjects with TEAEs by SOC and PT (only for subjects treated at right cheek volume).
- TEAEs affected left cheek volume, subjects with TEAEs by SOC and PT (only for subjects treated at left cheek volume).
- TEAEs affected both cheeks volume, subjects with TEAEs by SOC and PT (only for subjects treated at both cheeks volume).

Time to onset and duration of TEAEs will be listed.

Calculation of time to onset/duration of AEs (days):

- Time to onset of an AE is defined as start date of AE - date of first administration of study drug [+ 1 for AE starting after start of treatment]
- The duration will be calculated as stop date - onset date + 1.

Incomplete AE start and/or end date will not be replaced. Rules for separation of TEAE from non-TEAEs for missing or incomplete start dates are given in the Appendix M900391005-sap- appendix-v1.0.

In case of missing intensity or missing causal relationship of an AE the worst case principle will be applied, i.e. a missing intensity will be set to “severe” and a missing causal relationship will be set to “related”. Missing data of the worst outcome will be imputed by “unknown”. If a subject has more than one outcome within a PT only the worst outcome will be used in the frequency tables. Also on subject level, only the worst outcome category per subject will be counted in the frequency table. The worst outcome is defined in the following order:

- recovered/resolved
- recovered/resolved with sequelae
- recovering/resolving
- not recovered/not resolved
- unknown
- fatal.

In case of a subject with affected left and right nasolabial folds, with affected left and right marionette line or with affected left and right cheek volume within a PT the subject will be counted once under both nasolabial folds, under both marionette lines or under both cheeks, respectively. In case of a subject with at least one affected treatment area and one AE outside

treatment area within a PT the subject will be counted once under the respective affected treatment area.

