### **10.1.2 Adverse event handling and reporting**

Data pertaining to AEs will be collected during each investigation visit based on the subject's spontaneous description, through investigator inquiry, or discovered in the course of examinations done during the visit. The investigator will assess and record any AE in detail in the subject file and on the eCRF AE report form. The following information must be recorded:

- AE diagnosis or main symptom.
- Location of AE: systemic or restricted to injection area. In case of local reaction, the corresponding area should be reported.
- Date of onset.
- Date of worsening.
- Severity (maximum observed; see Section [10.1.3](#)).
- Causal relationship (not related, related).
- Serious (yes or no).
- Outcome (see Section [10.1.5](#)).
- Action taken with SMD
- AE leading to discontinuation of the investigation (yes or no).
- Stop date.

After completion of all scheduled visit assessments the investigator must document any AEs arising from these assessments.

In case of an serious adverse event (defined in section [10.2](#)), the investigator must also complete an SAE report form and report it to the CRO immediately, as described in Section [10.2.2](#).

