#### 12.4.2.1 Primary safety variable

The main analysis for the primary safety variable will be the overall TEAE incidence rate(s). Further incidences will be calculated for TEAEs on the system organ class level and on the preferred term level (i.e., total, by intensity, and by relationship, by outcome, and by injection site area). Listings and, if applicable, tables displaying incidences for TEAEs leading to discontinuation, serious TEAEs, and deaths will also be provided.

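### SAP 7.2.1 counts a subject with the same preferred term inside and outside a treated area only under the treated area, so the outside-area summary understates subjects per preferred term

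*SAP*

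**What the plan says.** Protocol 10.1.2 has the investigator record "Location of AE: systemic or restricted to injection area" for each adverse event and name the area for a local reaction. Protocol 12.4.2.1 asks for TEAE incidences by organ class and PT, broken down among other ways "by outcome, and by injection site area". It sets no order of precedence between locations.

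SAP 7.2.1 turns this into a set of tables by affected area. One is "TEAEs occurred outside treatment area, subjects with TEAEs by SOC and PT". The others cover right, left and both sides of each of the three indications.

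Two counting rules follow at the end of that section:

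- A subject with a PT on both left and right of one indication is counted once, in the row for both sides.
- The second rule begins "In case of a subject with at least one affected treatment area and one AE outside" and continues over the page: where both fall within one PT, "the subject will be counted once under the respective affected treatment area".

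There is a row for left plus right, but none for inside plus outside. SAP section 8 reports no change from the protocol's planned analyses.

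**The concern.** Under the second rule, a subject who had a PT in a treated area and also outside it does not appear in the outside-area row for that PT. The row is labelled as TEAEs outside the treatment area, but it holds only subjects whose PT occurred outside and nowhere inside. Nothing in the SAP text tells the reader so. The error runs in one direction: the rule can remove subjects from the row and never adds any.

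Safety is part of the primary objective, and Protocol 4.2 gives detection of emerging risks as one purpose of the study. A reader who takes the row at face value would get too low a figure for how many subjects had a given reaction away from the injected areas. The shortfall would tend to be largest for terms that are frequent inside those areas. Protocol 4.3 names swelling and redness as the commonest events in the earlier nasolabial-fold trial of this device, without giving their rates. The same tables are also planned for the Week 24/28 interim analysis (SAP 7.4.2).

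**Working it through.** **The plan's own safety figure.** SAP section 4 and Protocol 12.1 give an 80% chance of seeing a 1% adverse event at least once in 161 subjects. 1 − 0.99^161 = 0.8017, so the figure reproduces. The counting rule itself has no stated figure.

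**Inputs.** From the documents: the rule and the table (SAP 7.2.1), 210 subjects planned, and 161 completers per indication (SAP section 4). Not in the documents, so assumed: the incidence *a* of a PT inside treated areas (1% to 60%), its incidence *b* outside (5% in the table, 1% in the detection example), and the odds ratio OR between having the PT inside and outside (0.5 to 4).

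**Formula.** Let *p* be the probability that a subject has the PT in both locations.

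- Share of outside-area subjects lost = *p*/*b*, that is, P(same PT inside | PT outside).
- Under independence *p* = *ab*, so the share lost is *a*.
- Otherwise *p* = [S − √(S² − 4·OR·(OR − 1)·*ab*)] / [2(OR − 1)], with S = 1 + (*a* + *b*)(OR − 1).

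**Worked case.** With *a* = 0.40, *b* = 0.05 and OR = 4: S = 2.35, and *p* = (2.35 − √(5.5225 − 0.96))/6 = 0.0357. The share lost is 0.0357/0.05 = 71%.

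**Share of outside-area subjects lost, *b* = 5%:**

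| Inside incidence | OR 0.5 | OR 1 | OR 2 | OR 4 |
|---|---|---|---|---|
| 1% | 0.5% | 1.0% | 1.9% | 3.4% |
| 5% | 2.6% | 5.0% | 9.1% | 15.7% |
| 10% | 5.4% | 10.0% | 17.5% | 28.4% |
| 20% | 11.4% | 20.0% | 32.4% | 47.7% |
| 40% | 25.6% | 40.0% | 56.3% | 71.3% |
| 60% | 43.7% | 60.0% | 74.4% | 85.0% |

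**In subjects.** Of 210 subjects, 5% is 10.5 with the PT outside. Under independence the row loses 10.5 × 0.01 = 0.1 of them at 1% inside incidence, and 10.5 × 0.40 = 4.2 at 40%.

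**Chance that the row shows the PT at all.** Take a PT with 1% outside incidence in 161 subjects, under independence:

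- nothing lost: 1 − 0.99^161 = 80.2%
- 20% inside incidence: 1 − (1 − 0.008)^161 = 72.6%
- 40% inside incidence: 1 − (1 − 0.006)^161 = 62.1%

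**With the fix.** If these subjects are also counted in the outside-area row, the loss is 0% in every cell.

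**The case against.** The strongest reply is that this is a presentation choice, pre-specified and in keeping with the rest of the section, which also counts worst outcome and left-plus-right once per subject and PT. The main safety analysis is "Overall incidence of TEAEs", no test or stopping rule uses the outside-area row, and the effect can be trivial (0.1 of 10.5 subjects at 1% inside incidence). All of that stands and makes this a low priority. It does not remove the understatement: left-plus-right subjects keep a row of their own, whereas inside-plus-outside subjects have none.

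Four stronger readings are tempting, and the documents do not support them:

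- *That displacement or migration would be hidden.* The rule works within a PT, and Protocol 4.3 lists displacement/migration separately from swelling and erythema. If coded to its own PT, it leaves the outside-area row only when that same PT was also recorded inside.
- *That this is the only place where outside events can be seen.* Location is recorded for each event, the total tables by organ class and PT keep these events, and time to onset and duration are to be listed. The SAP also refers to an appendix of tables and listings that is not in the text available here, so a footnote or a location listing cannot be ruled out.
- *That events are dropped.* The rule governs subject counts. It is silent on event counts by area, and it mentions a single event outside, leaving several unaddressed.
- *That each lost subject is a spread signal.* The location field separates systemic events from those confined to the injection area, so the outside-area row may hold many systemic events.

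**Conclusion.** The point holds as a defect in one planned summary. For each PT, the outside-area row omits subjects who also had that PT in a treated area, so it understates the number of subjects with the PT outside. The direction follows from the rule alone and needs no assumed rate.

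The size does need assumptions. Under independence the loss equals the inside incidence. At 40% inside and 5% outside incidence it runs from about 26% to about 71% as the odds ratio goes from 0.5 to 4. That the commonest treated-area reactions lose most depends on a similar inside/outside association across PTs, which the documents neither state nor contradict.

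It would be wrong to infer that the study's main safety result is biased, since overall TEAE incidence and the total tables by organ class and PT do not use the rule.

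**What to change.** In SAP 7.2.1, leave the left/right rule as it is. Replace the inside/outside rule with one of these:

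1. Count a subject with the same PT inside and outside under the affected treated area and also in the outside-area row for that PT.
2. Keep the outside-area row for outside-only subjects, label it so, and add a row for subjects with the PT both inside and outside the treatment area.

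For option 1, add a footnote that a subject may appear in more than one location row. Overlap is not new to these tables: the SAP states no rule collapsing subjects across indications, so a subject with a PT in folds and cheeks can already appear under each. Say also that the rule covers one or more events outside, and state how event counts by area are handled if they are shown.

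The cost is a wording change, location rows that no longer separate inside from outside subjects (option 1) or one extra row (option 2), and a small change to the table programs for the interim and final analyses. No new data are needed, because location is already collected.

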7.2.2 Secondary Safety Variables

Not applicable.

Disposition of subjects

The absolute and relative frequencies for subject's main reason for premature study discontinuation will be tabulated, based on all enrolled subjects. Main reason "death" will be mapped to adverse event(s). Furthermore, the number of subjects screened, the number of subjects enrolled, the number of subjects enrolled and treated and the number of subjects in respective analyses sets will be displayed. For this study all enrolled subjects will be treated. Therefore, the number of subjects enrolled and the number of subjects enrolled and treated will be the same and screening failures are defined all as not treated subjects. The analysis will be performed in total and by the subpopulations of each indication.

Demographic data

Demographic data will be summarized in total and by subpopulations of each indication for the SES, the FAS, and the PPS. The following age categories will be analyzed:

- 18 - 64 years
- 65 - 84 years
- ≥ 85 years

Prior and concomitant medication and non-drug therapies

Separation of previous from concomitant therapies will be done according to the start and stop date of the therapy in comparison to the date of first injection. Each therapy will be allocated unambiguously either to previous therapies or to concomitant therapies.

- Previous therapy: If stop date is before start of treatment.
- Concomitant therapy: If the start date is at or after start of treatment. Or if the stop date is at or after start of treatment or ongoing is ticked.

Rules for separation of previous and concomitant medication for missing or incomplete dates are given in the Appendix M900391005-sap-appendix-final v1.0-2019-07-30.

Previous and concomitant medication will be coded by use of the World Health Organization (WHO) whereby the version in effect at the time the database is closed will be used for interim and final analysis.

Frequencies of previous and concomitant medication will be given on the basis of various Anatomical Therapeutic Chemical classification system of the World Health Organization (ATC) code levels for the SES, the FAS and the PPS. The analysis will be performed in total and by the subpopulations of each indication. Indications for concomitant therapies will not be coded and will only be listed.

Non-drug treatments will be coded using MedDRA version which is in effect at the time the database is closed. Non-drug treatments will be displayed by SOC and PT levels for the SES, the FAS and PPS. The analysis will be performed in total and by the subpopulations of each indication.

Medical history and concomitant diseases

Separation of medical history from concomitant diseases will be done according to the stop date of the finding in comparison to start of study treatment. Each finding will be allocated unambiguously either to medical history or to concomitant diseases.

- Medical history: If stop date is before start of treatment.

- Concomitant disease: If the stop date is at or after start of treatment or ongoing (even if it refers to a cut-off point before start of treatment) is ticked.

Rules for separation of medical history and concomitant diseases for missing or incomplete dates are given in the Appendix M900391005-sap-appendix-final v1.0-2019-07-30.

Medical history and concomitant diseases will be described on the basis of MedDRA SOC and PT levels for the SES, the FAS, and the PPS. The analysis will be performed in total and by the subpopulations of each indication.

Extend of exposure

Data of injection technique, depth of injections, volume and needles and cannulas will be analyzed separately for each indication for the corresponding subpopulation per treatment area (side) and in total for SES.

7.4 Special Statistical/Analytical Issues

7.4.1 Discontinuations and Missing Data

Discontinued subjects will not be replaced.

For responder analyses, missing values will be evaluated as non-responder (worst case replacement) for FAS. PPS will be used only for the primary performance analyses. Subjects with missing assessments with respect to the primary performance variables will be excluded from the PPS. Therefore no missing value replacement is needed for PPS.

Missing values for all further variables will not be imputed. All analyses except responder analysis [REDACTED] will be performed on observed cases only.

7.4.2 Interim Analyses

An interim analysis for the SES and the FAS will be performed including all data (safety, performance and other data) up to Week 24/28 respectively, depending on touch-up. The analyses of the subpopulations “nasolabial folds”, “marionette lines” and “cheek volume loss” is also part of the interim analysis. The PPS analysis is not part of the interim analysis and will be done for the final analysis at the end of the study in addition to SES and FAS. All tables and listings planned for the final analysis in the appendix will also be done for the interim analysis

up to the Visit V4 Week 24/28 except for the PPS tables and the table and listing for “Protocol deviations and other reasons for exclusion from analysis sets”.

The interim analysis will be done for obtaining the performance and safety data up to Week 24/28 as early as possible. Therefore, the purpose of this interim analysis is not to perform any adaptions on the study design, statistical analysis, sample size or for stopping the study, as this is not a study with an adaptive design.

Since this is an open label study, the interim analysis will not have any influence on the integrity of the study data and it will not bias the data collected after interim analysis.

7.4.3 Data Monitoring Committee

Not applicable.

7.4.4 Multiple Comparisons/Multiplicity

Three confirmatory tests will be performed in the primary analysis, one for each primary performance variable of the corresponding indication. Bonferroni Holm correction will be used to counteract the problem of multiple comparisons. For the three statistical test the local significance levels $\alpha_1=0.025/3$, $\alpha_2=0.025/2$ and $\alpha_3=0.025$ will be applied to obtain the global significance level of 0.025.

7.4.5 Examination of Subgroups

The subpopulation “nasolabial folds” will contain all subjects treated for nasolabial folds, regardless if they have been treated for one or both other indications as well. The subpopulation “marionette lines” will contain all subjects treated for marionette lines, regardless if they have been treated for only one or for two other indications as well. The subpopulation “cheek volume loss” will contain all subjects treated for cheek volume loss, regardless if they have been treated for one or both other indications as well. Each of these three subpopulations will contain approximately 175 subjects. Each subject will belong to at least two of these subpopulations. At least 50% of the subjects will be treated in all of the three indications and as consequence these subjects will belong to all of these three subpopulations (i.e. nasolabial folds, marionette lines, and cheek volume loss).

For the performance variables iGAIS, sGAIS, [REDACTED] [REDACTED] for subject dispositions, [REDACTED] [REDACTED], and for all safety analyses (analysis of TEAEs), subgroup analyses will be performed for each indication (subjects treated for nasolabial folds, for marionette lines and/or for cheek volume loss) in addition to the total population.

Responder analysis of MNLFS, MUCFS, and MMLS will only be performed for the subpopulations and not for the total population. [REDACTED] [REDACTED]

[REDACTED]™ – Satisfaction with Cheeks will only be analysed for the subpopulation “cheek volume loss”.

[REDACTED]

7.4.6 *Pooling of sites*

Not applicable.

8 CHANGES IN THE PLANNED ANALYSES

Not applicable.

Appendix 2: [REDACTED]

[REDACTED]

[REDACTED]

[REDACTED]
